9.1. Appendix A Standards for Variable Display in TFLs

Continuous Variables: The precision for continuous variables will be based on the precision of the data itself. The mean and median will be presented to one more significant figure than the original results; the SD will be presented to two more significant figures than the original results; the minimum and maximum will be presented to the same precision as the original results.

Categorical Variables: Percentages will be presented to 1 decimal place. If the count is 0, the percentage will not be displayed. If the count equals the denominator, the percentage will be displayed as 100.

9.2. Appendix B Analysis Visit Windows

Analysis visit windows will be utilized for immunogenicity assessments only.

Data will be mapped using the following approach:

Step 1: If the assessments are collected at a scheduled visit, the collected data will be mapped to the nominal scheduled visit.

Step 2: If the assessments are collected at an unscheduled visit or early termination visit, the collected data will be mapped using the analysis visit windows described in Table 3.

If a subject has multiple assessments within the same analysis visit, the following rule will be used:

- If multiple assessments occur within a given analysis visit, the assessment closest to the target study day will be used.
- If there are 2 or more assessments equal distance to the target study day, the last assessment will be used.

Table 3: Analysis Visit Windows for Immunogenicity Assessments

Study Arm	Visit	Visit Window in Study Day	Relative Date			
RSV nAbs and bAbs						
Arm 1	Day 1	1	Date of Day 1 Injection			
Arm 1	Day 22	[15, 36]	Date of Day 1 Injection			
Arm 2	Day 22	1	Date of Day 22 Injection			
Arm 2	Day 43	[15, 36]	Date of Day 22 Injection			
Influenza anti-HA Abs by HAI assay						
Arm 1 and Arm 2	Day 1	1	Date of Day 1 Injection			
Arm 1 and Arm 2	Day 22	[15, 36]	Date of Day 1 Injection			

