8. STUDY ASSESSMENTS AND PROCEDURES

- Study procedures and their timing are summarized in the SoA (Table 1). Protocol waivers or exemptions are not allowed.
- Adherence to the study design requirements, including those specified in the SoA (Table 1), is essential and required for study conduct.
- All screening evaluations must be completed and reviewed to confirm that potential participants meet all eligibility criteria. The Investigator will maintain a screening log to record details of all participants screened and to confirm eligibility or record reasons for screening failure, as applicable.
- Procedures conducted as part of the participant's routine clinical management (eg, blood count) and obtained before signing of the ICF may be utilized for screening or baseline purposes provided the procedures met the protocol-specified criteria and were performed within the timeframe defined in the SoA (Table 1).
- In the event of a significant study-continuity issue (eg, caused by a pandemic), alternate strategies for participant visits, assessments, medication distribution, and monitoring may be implemented by the Sponsor or the Investigator, as per local health authority/ethics requirements.
- Study results that could unblind the study will not be reported to investigative sites or other blinded personnel until the study has been unblinded.
- If a visit cannot be scheduled within the indicated allowable window and/or the participant misses the visit, this is considered a protocol deviation. However, the visit should still be completed, if possible, to collect study data. Subsequent visits should be scheduled at the originally planned number of days after Day 1 defined in the SoA (Table 1).

The maximum amount of blood collected from each participant over the duration of the study, including any extra assessments that may be required, will not exceed blood limits specified by local regulations. Sample collection on Day 1 and Day 22 (ie, blood) must be performed prior to study intervention dosing.

Repeat or unscheduled samples may be taken for safety reasons or for technical issues with the samples. Further details are provided in both the ICF and Laboratory Reference Manual.

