- A complete physical examination, including height and weight, will be performed at the Screening Visit. Symptom-directed physical examinations will be performed at other study visits, if clinically indicated (see protocol Section 8.3.1 for additional details).
- d. Vital sign measurements include assessment of systolic and diastolic blood pressure, pulse rate, respiratory rate, and body temperature (preferred route is oral) (see protocol Section 8.3.2 for additional details).
- Blood samples for humoral immunogenicity must be collected prior to administration of the study intervention on Day 1 and Day 22.
- All participants will be randomized to receive 2 IM injections, one in each arm, in the deltoid muscle (Day 1) and 1 IM injection in the deltoid muscle (Day 22).
- At Day 1 and Day 22, eDiary instruction will be provided while the participant is onsite. The participant will be required to make eDiary entries approximately 30 minutes after each vaccination while at the study site and again that same evening when at home. Study participants will continue to record in the eDiary each day at the same time for 6 days following each vaccination. Local solicited ARs will be recorded separately for each injection. eDiary review by the site should occur daily on Day 1-Day 7 and Day 22-28. Additional review of the eDiary will occur at Day 8 and Day 29 between the site and the participant during the safety telephone calls.
- h. Medically qualified study staff will contact all participants. The participant will be interviewed according to the script. Information will be collected about occurrence of unsolicited AEs through 21 days postvaccination for either RSV or influenza, and the occurrence of MAAEs, SAEs,

Confidential Page 40
Document Number: VV-CLIN-015611 eDMS Version: 2.0

AESIs, or AEs leading to study discontinuation and concomitant medications associated with those events, and receipt of any nonstudy vaccinations at all points of contact.

Date Issued: 10-Nov-2023

All concomitant medications and procedures will be recorded for 21 days following each vaccination (Day 1 through Day 43); all nonstudy vaccinations and concomitant medications relevant to or for the treatment of an SAE, AESI, or MAAE will be recorded from Day 1 through Month 6 after the last study injection/EoS.

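### The HAI Day 22 analysis window does not end at the Day 22 injection, so in rare Arm 2 cases a serum drawn after mRNA-1345 could serve as the pre-mRNA-1345 control titer.

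*SAP*

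**What the plan says.** Four of the six coprimary endpoints compare HAI GMTs between arms at Day 22 (SAP 4.2). By then Arm 1 has had Fluzone HD with mRNA-1345, and Arm 2 has had Fluzone HD with placebo. Arm 2 receives mRNA-1345 at the Day 22 visit (Protocol 6.1), which the Schedule of Activities allows up to 7 days late, so on study days 22 to 29.

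SAP 9.2, Appendix B assigns samples in two steps:

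- Scheduled draws: "the collected data will be mapped to the nominal scheduled visit".
- Other draws: "If the assessments are collected at an unscheduled visit or early termination visit, the collected data will be mapped using the analysis visit windows" in Table 3. The HAI row reads "Arm 1 and Arm 2 Day 22 [15, 36] Date of Day 1 Injection".

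If several samples fall in one analysis visit, "If multiple assessments occur within a given analysis visit, the assessment closest to the target study day will be used". Ties are settled by a further rule: "If there are 2 or more assessments equal distance to the target study day, the last assessment will be used".

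SAP 6.1 confirms that unscheduled measurements enter scheduled visits through these windows. Protocol Section 8 foresees such draws: "Repeat or unscheduled samples may be taken for safety reasons or for technical issues with the samples". The rule on timing relative to dosing is: "Blood samples for humoral immunogenicity must be collected prior to administration of the study intervention on Day 1 and Day 22".

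**The concern.** The Arm 2 HAI titer at Day 22 is meant to show the response to Fluzone HD before any mRNA-1345. The scheduled draw secures this because it is pre-dose. The analysis window does not, because its upper limit of study day 36 is counted from the Day 1 injection and ignores when the Day 22 injection was given.

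An Arm 2 redraw after that injection therefore supplies a titer from someone who has already received mRNA-1345. An Arm 1 redraw on the same day follows only placebo, so the problem arises in one arm only.

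All six coprimary endpoints must succeed for the study to succeed (SAP 6.5), and this row feeds four of them.

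**Working it through.** **1. Window arithmetic.** Study days 15 to 36 are 36 − 15 + 1 = 22 days. If Arm 2 is dosed on Day 22, days 23 to 36 follow mRNA-1345: 14 of 22. If dosed on Day 29, days 30 to 36 follow it: 7 of 22. These are calendar days open to a sample, not a count of samples.

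**2. When a post-dose sample would be selected in Arm 2.** Table 3 names no target day; Day 22 is assumed.

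- *No usable pre-dose result.* An unscheduled redraw after dosing, up to day 36, is mapped to Day 22. If it is the only result there, it is used.
- *Repeat on the injection day, after dosing.* Both samples are equally far from target and the later one is used. Such a draw would also breach the pre-dose rule.
- *Day 22 visit held early, itself a deviation.* With a visit on day 20, an unscheduled draw on days 21 to 23 is closer to target, and one on day 24 ties and is later.
- *Valid pre-dose result from day 22 or later, extra draw on a later day.* The extra draw is further from target and is not used.
- *Scheduled Day 43 draw.* It keeps its nominal visit and cannot become a Day 22 value.

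**3. Whether another rule removes the sample in the first case.**

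| Rule | Effect on an Arm 2 redraw on, say, day 28 after dosing on Day 22 |
|---|---|
| Pre-dose draw rule (SAP Appendix F; Protocol 8) | Governs the Day 1 and Day 22 collections; does not address a later redraw |
| PP exclusion of out-of-window results (SAP 5.3) | Uses the Appendix B window; day 28 is inside |
| IcEv4 (SAP Appendix G, Table 4) | Same window; not triggered |
| PP exclusion for missing baseline (SAP 6.2.7) | Not necessarily triggered: the Arm 2 RSV baseline is the latest result up to the Day 22 injection, so Day 1 can serve |
| FAS analysis | Keeps all data under treatment policy |

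**4. The plan's power figure.** Inputs from SAP 4.3: 855 per arm, SD 1.5 on the natural-log scale, GMR 0.9, margin 1.5, two-sided alpha 0.05.

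- SE = 1.5 × √(2/855) = 0.0725
- Distance from the margin = ln 0.9 − ln(1/1.5) = 0.3001
- Power = Φ(0.3001/0.0725 − 1.960) = 98.5%, as stated
- Overall = 0.985⁶ = 91.3%, as stated (91.5% from the unrounded value)

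**5. Illustration of the bias.** All three assumptions come from outside the documents: a fraction f of Arm 2 titers is affected, each carries the full coadministration effect, and the true GMR is at the margin.

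- Expected GMR = (1/1.5)^(1−f)
- One-sided error = Φ(f × ln 1.5 / 0.0725 − 1.960)

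| f (assumed) | Arm 2 participants of 855 | Expected GMR | One-sided error per strain |
|---|---|---|---|
| 0 | 0 | 0.667 | 0.0250 |
| 1% | about 9 | 0.669 | 0.0285 |
| 2% | about 17 | 0.672 | 0.0323 |
| 5% | about 43 | 0.680 | 0.0464 |

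**6. Power after the fix.** Suppose it removes a share f of Arm 2, so SE = 1.5 × √(1/855 + 1/(855(1 − f))). Overall power applies the loss to all six endpoints, which is pessimistic because only the four HAI endpoints lose data.

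| f (assumed) | Power per endpoint | Overall power |
|---|---|---|
| 0.5% | 98.5% | 91.4% |
| 1% | 98.5% | 91.3% |
| 2% | 98.4% | 91.0% |
| 5% | 98.3% | 90.3% |

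**The case against.** The case that this is negligible has real strength.

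- **Safeguards.** Protocol 8.2 plans aliquots so that backup material exists, which makes a wholly unusable Day 22 sample less likely. Scheduled draws keep their nominal visit. A valid pre-dose result from day 22 or later beats any draw on a later day. No scheduled blood draw falls between Day 22 and Day 43. These points stand and confine the problem to rare cases.
- **Early termination.** Step 2 names early-termination samples, but Protocol 7.2 asks for a call at discontinuation and the Schedule of Activities has no blood draw there. That route adds little.
- **Open list of exclusions.** SAP 6.2.7 lets the sponsor add PP exclusions before database lock and unblinding. Such cases could be caught there, but the SAP does not commit to it.
- **The RSV rows.** Arm 2's Day 22 RSV row is tied to the injection date because that sample is a baseline. It is not evidence that a safeguard was intended for HAI and then forgotten.

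Two stronger readings are tempting and are not supported. A reader might infer that any effect of mRNA-1345 makes the error anti-conservative. That holds only if mRNA-1345 lowers HAI titers; if it raises them, a GMR above 1 is pulled down toward 1 and the lower bound falls. A reader might also infer that the control arm then has the exposure under test. The exposure under test is coadministration. An Arm 2 participant bled on day 28 is still on the assigned sequential regimen, and the documents do not show that mRNA-1345 given about three weeks after Fluzone HD acts on HAI titers as same-day dosing does.

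**Conclusion.** The gap is real but narrow. As written, Table 3 can admit a post-mRNA-1345 titer as the Arm 2 HAI Day 22 value, and no other stated rule reliably removes it. This rests on the literal text of Appendix B and on Day 22 being the target day.

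The likely effect is small. The documents give no redraw rate and neither the sign nor the size of any mRNA-1345 effect on HAI at this interval. In the direction that noninferiority must rule out, affected samples would favour the noninferiority claim; in the other direction they would work against it. The error rates of 0.0285 to 0.0464 depend on the full-effect assumption and an assumed 1% to 5% of Arm 2 affected. They illustrate a mechanism and do not estimate what will happen in this trial.

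The stated sample size and power are unaffected. This is a minor clarification, worth making before unblinding because it concerns coprimary contrasts.

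**What to change.** In the HAI Day 22 row of Table 3, for both arms, require the sample to lie in [15, 36] and, when a Day 22 injection is given, to be collected before it, comparing date and time where available. If no Day 22 injection is given, the whole window stays open. In the PP analysis, treat later samples as out of window under IcEv4. State the target study day in the table.

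Applying the rule to both arms keeps sample selection symmetric. The cost is a few redrawn titers lost from the PP analysis, with the small power loss shown above. The FAS analysis would still include these titers under treatment policy, so flag them there and report their number by arm.

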9.3. Appendix C Imputation Rules for Missing Dates of Prior/Concomitant Medications

Imputation rules for missing or partial start/stop dates of medication are defined below:

- 1. Missing or partial medication start date:
 - If only Day is missing, use the first day of the month, unless:
 - The medication end date is on/after the date of the injection or is missing/partial AND the start month and year of the medication coincide with the start month and year of the injection. In this case, use the date of the injection.
 - If Day and Month are both missing, use the first day of the year, unless:
 - The medication end date is on/after the date of the injection or is missing/partial AND the start year of the medication coincide with the start year of the IP injection. In this case, use the date of the injection.
 - If Day, Month, and Year are all missing, the date will not be imputed, but the medication will be treated as though it began prior to the injection for purposes of determining if status as prior or concomitant.
- 2. Missing or partial medication stop date:
 - If only Day is missing, use the earliest date of (last day of the month, study completion, discontinuation from the study, or death).
 - If Day and Month are both missing, use the earliest date of (last day of the year, study completion, discontinuation from the study, or death).
 - If Day, Month, and Year are all missing, the date will not be imputed, but the medication will be flagged as a continuing medication.

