6.2.4. Prior and Concomitant Medications

Any medication or vaccine (including OTC or prescription medicines, recreational drugs, vitamins, and/or herbal supplements) or other specific categories of interest that the participant is receiving at the time of enrollment or receives during the study will be recorded in the participant's eCRF. Specific categories of interest are detailed in the section 6.9 of the study protocol.

Prior and concomitant medications will be coded using the World Health Organization (WHO) drug dictionary (WHO-DD). The summary of concomitant medications will be based on the Safety Set. Imputation rules for missing/partial dates for medications is detailed in Appendix C.

For analysis purpose, a medication taken prior to the Day 1 injection date, regardless of whether the end date is before or after the injection date, is defined as "prior"; if the medication is taken on or after the Day 1 injection date through Month 6/EoS visit, then it is considered "concomitant", regardless of whether the start date is before or after the injection date.

An overall summary table of concomitant medications and non-study vaccinations will be provided to present the number and percentage of participants who take the following:

- Any concomitant medications and non-study vaccinations within 7 days post any injection
- Any concomitant medications and non-study vaccinations within 21 days post any injection
- Any non-study vaccinations within 7 days post any injection
- Any non-study vaccinations within 21 days post any injection
- Any prophylactic antipyretics or analgesics medication within 21 days post any injection
- Any antipyretic or analgesic medication within 21 days post any injection

A summary table of concomitant medications and non-study vaccinations within 21 days post any injection will be provided by ATC level 2 and PT. PT will be displayed in descending order of frequency of the "D1: Fluzone HD+mRNA-1345 (µg) and D22: placebo" group. A separate summary table of non-study vaccinations within 7 days post any injection will be also provided by PT.

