9.5. Appendix E Imputation Rules for Missing Dates of AEs

Imputation rules for missing or partial start dates and stop dates of AEs are defined below:

- 1. Missing or partial start date:
 - If only Day is missing, use the first day of the month, unless:
 - The AE end date is on/after the date of the injection or is missing/partial AND the start month and year of the AE coincide with the start month and year of the injection. In this case, use the date of the injection.
 - If Day and Month are both missing, use the first day of the year, unless:
 - The AE end date is on/after the date of the injection or is missing/partial AND the start year of the AE coincides with the start year of the injection. In this case, use the date of the injection.
 - If Day, Month, and Year are all missing, the date will not be imputed. However, if the AE end date is prior to the date of the injection, then the AE will be considered a pretreatment AE and will not be included in the AE analyses. Otherwise, the AE will be included in the AE analyses.
- 2. Missing or partial end dates will not be imputed.

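### In the year-only branch of SAP Appendices C and E, a partial end date from a month before the injection still moves the start to the injection day, so the record starts after it stopped

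*SAP*

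**What the plan says.** **Medication start (SAP 9.3, Appendix C).** The default for a start with neither day nor month is given as "If Day and Month are both missing, use the first day of the year, unless" an exception applies. The exception is "The medication end date is on/after the date of the injection or is missing/partial AND the start year of the medication coincide" with the year of the injection, in which case the injection date is used. The branch with only the day missing has a parallel exception, where the end date "is missing/partial AND the start month and year of the medication coincide with the start month and year of the injection".

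**Medication stop (same appendix).** "If only Day is missing, use the earliest date of (last day of the month, study completion, discontinuation from the study, or death"). A stop with a known month is therefore never imputed later than the last day of that month.

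**Adverse events (SAP 9.5, Appendix E).** The year-only start branch uses the same test: "The AE end date is on/after the date of the injection or is missing/partial AND the start year of the AE coincides" with the injection year. Missing or partial end dates of events are not imputed. When the start is missing altogether, the end date is compared with the injection: "if the AE end date is prior to the date of the injection, then the AE will be considered a pretreatment AE".

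**Classification (SAP 6.2.4).** A medication taken before the Day 1 injection date is prior. For the other class, "if the medication is taken on or after the Day 1 injection date through Month 6/EoS visit, then it is considered" concomitant. A medication can be both.

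**The concern.** A partial end date is not the same as no end date. If its month is known and lies before the injection month, it already proves that the record ended before the injection. The exception treats it as uninformative and gives the record a start that its own stop date rules out. A complete end date in the same month would have been handled correctly, so losing the day of the month overrides evidence that settles the order.

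Appendix E is also uneven. With no start date at all, an end date before the injection makes the event pretreatment. With a start year known, which is more information, a partial end date in an earlier month is ignored and the event is placed on the injection day.

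At stake is whether a few pre-injection medications are reported as taken within 7 or 21 days after injection, and whether a pre-injection event could be counted as occurring on the day of injection.

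**Working it through.** The plan gives no figure to reproduce here. The check applies the stated rules literally.

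**Inputs.** The start and stop rules come from SAP 9.3 and the event rule from SAP 9.5. Classification comes from SAP 6.2.4. Prior medications are collected for the 28 days before consent (Protocol 6.9), and screening is up to 28 days before Day 1 (Protocol 1.3, Table 1). The injection dates are assumptions, and the injection is read as Day 1.

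**Step 1, the rule.** Let J be the injection date, S the start year and E the end date.
- Imputed start = J if S = year(J) and (E ≥ J, or E is missing, or E is partial); otherwise 1 January of S.
- Imputed stop, month known, before the injection month = last day of that month. Study completion, discontinuation and death all fall on or after J, so they do not bind.
- The order reverses when J is later than the last day of the stop month, that is, when the stop month precedes the injection month in the same year.

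**Step 2, worked cases.**

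| Start | End | Injection | Imputed start | Imputed (or given) stop | Order |
|---|---|---|---|---|---|
| 2023 | Sep 2023 | 20 Oct 2023 | 20 Oct 2023 | 30 Sep 2023 | start 20 days after stop |
| 2023 | Aug 2023 | 20 Oct 2023 | 20 Oct 2023 | 31 Aug 2023 | start 50 days after stop |
| 2023 | Mar 2023 | 15 Oct 2023 | 15 Oct 2023 | 31 Mar 2023 | reversed |
| 2023 | 20 Mar 2023 (complete) | 15 Oct 2023 | 1 Jan 2023 | 20 Mar 2023 | correct |
| 2022 | Mar 2023 | 15 Oct 2023 | 1 Jan 2022 | 31 Mar 2023 | correct |
| Oct 2023 | Oct 2023 | 15 Oct 2023 | 15 Oct 2023 | 31 Oct 2023 | correct |

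Rows 3 and 4 differ only in whether the day of the end date is known.

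**Step 3, extent.** The rules were run on every logically possible pair of partial start and partial end dates in 2022 to 2024 whose end lies before the injection month. Entries are reversed pairs out of all such pairs.

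| Start / end | Injection 15 Oct 2023 | 6 Nov 2023 | 10 Jan 2024 |
|---|---|---|---|
| Year only / month known | 9 of 30 | 10 of 32 | 0 of 36 |
| Month known / month known | 0 of 231 | 0 of 253 | 0 of 300 |
| Month known / year only | 0 of 12 | 0 of 12 | 0 of 36 |
| Year only / year only | 0 of 1 | 0 of 1 | 0 of 3 |

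Only the year-only start with a month-known end fails. With only the day missing, a start in the injection month cannot have an end in an earlier month. A January injection has no earlier month in its own year.

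**Step 4, what is collected.** For an injection on 20 October 2023, the earliest consent is 20 Oct − 28 days = 22 Sep. The earliest collected medication stop is 22 Sep − 28 days = 25 Aug. Of the nine stop months from January to September, only August and September are reachable for medications: 2, not 9.

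**Step 5, classification.** With imputed start 20 October and stop 30 September, the start is no longer before Day 1, so by start date the drug is not prior. Code keyed on the start counts it as concomitant. Code that also requires the stop to be on or after Day 1 places it in neither class. Neither result fits a drug known to have stopped in September.

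**The case against.** **Stops could be imputed first.** A programmer might impute the stop and then find that the end date is no longer partial. Appendix C does not say so. It lists starts before stops, and its exception names partial end dates explicitly. For events this route is closed, because Appendix E imputes no end dates. The objection does not stand.

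**The reach is small.** This stands. A reader might take the nine reversed months in the October enumeration as the practical exposure, but the collection window leaves about two for medications. Vaccines have a longer look-back (12 months, Protocol 6.9). A vaccination is a single-day act, however, so a known stop month with an unknown start month is implausible.

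**Classification as concomitant is not certain.** This stands. A reader might infer that every such drug enters the 7-day and 21-day tables. SAP 6.2.4 also permits a test on the stop date, which would keep it out. What the text guarantees is contradictory dates.

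**PP Set.** A reader might infer that misdated immune-modifying drugs would remove participants from the PP Set. The documents do not support this. SAP 6.2.7 has the sponsor determine and document exclusions before database lock and unblinding, and nothing ties that decision to imputed dates.

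**Adverse events.** A reader might infer a general inflation of event counts. Protocol 8.4.1 sends non-serious events between consent and dosing to medical history. SAP 6.3.2 limits analysed events to those not present before exposure. What remains is mainly a serious event between consent and Day 1 that ended in an earlier month and has a year-only start. With serious events reported within 24 hours, that should be rare.

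**Conclusion.** Wrong as written, minor. In the year-only start branch of Appendices C and E, the stated rule produces an impossible order of dates whenever the end date is partial and its month is known and earlier than the injection month in the same year. No other text in either appendix checks the order.

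The number of affected records cannot be derived from the documents and is likely to be small. The consequence is confined to the descriptive medication summaries and, rarely, to a pre-injection serious event. The gap of 20 days in the example is only a date difference; the SAP plans no summary of medication duration. No effect on the PP Set, the coprimary endpoints or the tested secondary endpoints is shown.

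The size rests on the assumed autumn 2023 injection dates and on reading the injection as Day 1. The appendices do not say which injection is meant, and exposure could be wider if it were Day 22.

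**What to change.** In the year-only start branch of Appendix C and of Appendix E, replace the missing/partial condition with: *or is missing, or is partial and its latest possible date is on/after the date of the injection*. Otherwise keep the first day of the year. Add to both appendices that an imputed start must never fall after the imputed or latest possible end.

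Under this change, start 2023 with stop March 2023 and an injection on 15 October 2023 gives 1 January 2023 to 31 March 2023, and the medication is prior only. The reversed pairs in the enumeration fall from 9 (October) and 10 (November) to 0.

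The cost is one clause and one check per appendix and a line of code. No endpoint, hypothesis or sample size changes.
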